# 1. Overview of analysis

This document contains the statistical analysis plan for "Can a tailored quality assurance program help general practitioners maintain POCUS scanning competence?: A cohort study from Denmark". The study protocol (ClinicalTrials.gov ID NCT05625646) specified the intended analyses *prior to collection of the primary outcome*. This document elaborates on these intended analyses to be performed in the main study paper.

This study is a follow-up of a prior study (ClinicalTrials.gov ID NCT05274581) in which 18 general practitioners completed a tailored ultrasound educational program and had their ultrasound scanning competences assessed immediately after the program and at follow-up after three months. The three-month follow-up in the previous study is baseline for the present study.

Hence, data for the present study were gathered between September 7th 2022 and January 22nd 2024. Scanning competence scores were collected at baseline (September 7th and November 3rd 2022) and after 14 months (November 30th 2023 and January 22nd 2024). Quarterly quizzes were collected in: December 2022/January 2023(Quiz 1), March/April 2023(Quiz 2), August/September 2023(Quiz 3) and October/November 2023(Quiz 4). Remuneration fess for performed ultrasound scans were collected between November 2022 and November 2023. Background characteristic on participating general practitioners were collected on March 3rd 2022 when participants enrolled in the previous study and updated for the present study.

# 2. Setting

The study is conducted in Danish general practice where office-based general practitioners practice family medicine and use ultrasound to examine patients with relevant conditions. Prior to the study, all participating general practitioners have completed an ultrasound educational program at a training facility and the data collection for the primary outcomes will be collected at the training facility.

### 2.1 Eligibility

#### 2.1.1 inclusion criteria

To be eligible for the study, subjects must fulfil the following criteria:

- 1. Be a postgraduate medical doctor with a specialization in general practice.
- 2. Work in office-based general practice in Denmark
- 3. Have access to an ultrasound device in the practice during the study period
- 4. Have completed the ultrasound educational program in the previous study

#### 2.1.2 exclusion criteria

To be eligible for this study, subjects must not meet any of the following criteria:

- 1. Have a possible conflict of interest (e.g., industry affiliation related to the use of ultrasound)
- 2. No signed informed consent to participate.

### 3. Adherence

During the study, CAA monitored participants' scanning activity and responses to the quizzes and reached out to participants failing to be active or failing to complete the quizzes.

## 4. Background characteristics

Tables of summary statistics will be produced in one group. The table will include:

Variable	Unit	Description
Age	Years	Mean (SD) or median (IQR)
Sex	Male, female, other	Frequency (%)
Previous use of	Number of months with	Mean (SD) or median (IQR)
ultrasound	regular use	
Previous ultrasound	Yes, no	Frequency (%)
courses of minimum 1		
day duration		
Scanner type	Low range, mid range,	Frequency (%)
	high end	
Type of practice	Collaboration,	Frequency (%)
	partnership, solo	
Location of practice	Urban, rural, mixed	Frequency (%)
Number of patients	1000-20000	Mean (SD) or median (IQR)
assigned to the practice,		
Number of GPs working in	1-20	Mean (SD) or median (IQR)
the practice.		

# 5. Outcomes

### 5.1 Primary outcomes

For the primary outcomes P1 and P2 and the secondary outcomes S1 and S2, we will use the Objective Structured Assessment of Ultrasound Skills (OSAUS) score collected at baseline and at follow-up.

The OSAUS assessment tool has been developed and validated as a generic tool for assessing scanning competence (3). The OSAUS scale consists of seven items: 'indication for the examination', 'applied knowledge of ultrasound equipment', 'image optimization', 'systematic examination', 'interpretation of images', 'documentation of the examination' and 'medical decision-making'. Each item is rated using a five-point Likert-scale with descriptions of performance ranging from very poor (score = 1) to excellent (score = 5). Hence, for each scanning modality a total score from 7 to 35 points may be achieved.

**Primary outcome 1 (P1):** The summarized OSAUS score at follow-up for all ten modalities will be calculated as percentage of maximum score. To summarize normal and non-normal distributed data similarly mean (SD) as well as median (IQR) will be presented together with minimum and maximum scores.

**Primary outcome 2 (P2):** The summarized OSAUS score at follow-up for each participating GP will be compared to the OSAUS sum score at baseline. The mean difference will be reported along with the proportion of GPs, with an OSAUS sum score at follow-up larger than or equal to the ultrasound competence score at baseline.

### 5.2 Secondary outcomes

**(S1):** For GPs, participating in a POCUS quality assurance program, the OSAUS item scores at follow-up, for each of the ten scanning modalities included in the curriculum will be calculated and presented as median, IQR, minimum and maximum score.

**(S2):** For GPs, participating in a POCUS quality assurance program, the proportion of GPs, who achieve a minimum OSAUS item score of three for all seven items for each of the ten scanning modalities at follow-up will we reported.

For the secondary outcome **S3**, we will use the GPs assessment of their own scanning competence. The GPs will declare to which degree they have POCUS scanning competence within a specific scanning modality to perform the scan un-supervised in

general practice (To a very high degree, to a high degree, to some degree, to a lesser degree, not at all, unsure).

**(S3):** For GPs, participating in a POCUS quality assurance program, the proportion of GPs, who rate themselves as competent to perform POCUS un-supervised in general practice at follow-up, within each of the ten scanning modalities.

For the secondary outcome **S4**, we will use fee-specific codes registered by the GP during consultation in general practice. Following the use of POCUS in the general practice consultations the GPs will follow normal procedures for registration of activities in general practice using remuneration codes and fee-specific codes for using POCUS in the medical record system. Prior to this study, 10 fee-specific codes for the 10 different POCUS examinations in the curriculum will be installed in the medical record system. The Primary Sector Data Provider Platform (PLSP) will develop an algorithm that allows for the following data extraction on each participating GP in a given time frame: (1) number of POCUS examinations performed and (2) number of consultations. PLSP will deliver monthly aggregated data for each participating GP from baseline to 12 months after baseline.

**(S4):** The number of monthly performed POCUS examinations by each GP from baseline to follow-up will be summarized to demonstrate monthly variation over time.

For the secondary outcome **S5** and **S6**, we will use the results of distributed online quizzes to the participants. During the study, four online quizzes will be sent to participants by email (Months 3, 6, 9, and 12). A reminder will follow after two weeks to participants who fail to respond the quiz.

**(S5):** For GPs, participating in a POCUS quality assurance program, the absolute number and proportion of GPs, who complete the online quiz at months 3, 6, 9 and 12 will be reported.

**(S6):** The results of the online quizzes at months 3, 6, 9 and 12 after baseline will be summarized and reported as tests scores for GPs, participating in a POCUS quality assurance program will be reported.

**(S7)**: For GPs, participating in a POCUS quality assurance program, we will graphically illustrate the relationship between total number of performed POCUS examinations for each of the ten scanning modalities included in the curriculum and OSAUS sum score at follow-up.

**(S8):** For GPs, participating in a POCUS quality assurance program, we will graphically illustrate the relationship between the number of completes quizzes in the quality assurance program and OSAUS sum score at follow-up.

**(S9):** For GPs, participating in a POCUS quality assurance program, we will graphically illustrate the relationship between the test score in the quizzes in the quality assurance program and OSAUS sum score at follow-up.

**(S10):** For GPs, participating in a POCUS quality assurance program, we will graphically illustrate the relationship between the OSAUS sum score at baseline and OSAUS sum score at follow-up.

**(S11):** the evaluation made by GPs, participating in a POCUS quality assurance program, will include:

- The absolute number and proportion of participants, who think the online quizzes helped them maintain scanning skills over the past year.

- The absolute number and proportion of participants, who think the online quizzes helped maintain focus on ultrasound over the past year.

- The absolute number and proportion of participants, who think the online quizzes developed their scanning skills over the past year.

- The absolute number and proportion of participants, who think the online quizzes were manageable in terms of time.

- The absolute number and proportion of participants, who think the online quizzes were manageable in terms of content.

- The absolute number and proportion of participants, who were overall satisfied with the online quizzes.

- The absolute number and proportion of participants, who think the OSAUS assessments have helped them maintain scanning skills over the past year?

- The absolute number and proportion of participants, who think the OSAUS assessments have developed their scanning skills over the past year.

- The absolute number and proportion of participants, who were overall satisfied with the OSAUS assessments.

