(P1): The summarized OSAUS score after 12 months for all ten modalities will be calculated as percentage of maximum score. To summarize normal and non-normal distributed data similarly mean(SD) as well as median(IQR) will be presented together with minimum and maximum scores.

Primary outcome 2 (P2):

The summarized OSAUS score at baseline and at 12 months for each participating GP will be compared and the proportion of GPs, with an OSAUS score at 12 months larger than or equal to the ultrasound competence score at baseline, will be reported.

Secondary outcomes

(S1): For GPs, participating in a POCUS quality assurance program, the OSAUS scores and the item scores after 12 months, for each of the ten scanning modalities included in the curriculum will be calculated and presented as median, IQR, minimum and maximum score.

(S2): We calculate the proportion of GPs, who achieve a minimum OSAUS score of three for all seven domains for each of the ten scanning modalities after 12 months. As variation in scores can occur between the four expert assessors. We will normalize the scores by multiplying a given accessors score with (0.2 x sum of scores of all five accessors/the given accessors mean score) prior to calculating the proportion of successful GPs.

For the secondary outcome S3, we will use the GPs assessment of their own scanning competence. The GPs will declare to which degree they have POCUS scanning competence within a specific scanning modality to perform the scan un-supervised in general practice (To a very high degree, to a high degree, to some degree, to a lesser degree, not at all, unsure).

(S3): We calculate the proportion of GPs, who rate themselves as competent to perform POCUS un-supervised in general practice, after the educational period (three months after baseline), within each of the ten scanning modalities.

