For the secondary outcome S4, we will use fee-specific codes registered by the GP during consultation in general practice. Following the use of POCUS in the general practice consultations the GPs will follow normal procedures for registration of activities in general practice using remuneration codes and fee-specific codes for using POCUS in the medical record system. Prior to this study, 10 fee-specific codes for the 10 different POCUS examinations in the curriculum will be installed in the medical record system. The Primary Sector Data Provider Platform (PLSP) will develop an algorithm that allows for the following data extraction on each participating GP in a given time frame: (1) number of POCUS examinations performed and (2) number of consultations. PLSP will deliver monthly aggregated data for each participating GP from baseline to 12 months after baseline.

(S4): The number of performed POCUS examinations by each GP each month during the study (months 1-12 after baseline) will be summarized to demonstrate variation over time.

For the secondary outcome S5 and S6, we will use the results of distributed online quizzes to the participants. During the study, four online quizzes will be send to participants by email (Months 3, 6, 9, and 12). A reminder will follow after two weeks to participants who fail to respond the quiz. The results of these quizzes will be summarized as the total number of completed quizzes for each participant (S5) and the test score for each participant at months 3, 6, 9, and 12 (S6).

For the secondary outcomes S7, S8 and S9, we will use a linear regression model to test associations between OSAUS score after 12 months and the total number of performed POCUS examination for each scanning modality (S7), the number of completed quizzes in the quality assurance program (S8), and the tests scores in the quality assurance program (S9). Changes in OSAUS scores between baseline and 12 months (S10) are calculated using linear regression. Scores at baseline and after 12 months will also be compared by a paired t-test.

13 Time schedule

Figure 2 Study timeline

	2022							2023														
Month	Mar	Apr	May	Jun	Jul	Aug	Sep	Oct	Nov	Dec	Jan	Feb	Mar	Apr	May	Jun	Jul	Aug	Sep	Oct	Nov	Dec
Ultrasound course																						
Skills assessment																						
Registration of fee for using POCUS																						
Quiz																						
Evaluation																						

14 Sample size

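### SAP S1 no longer lists the modality OSAUS score pre-specified in the protocol, and S7, on its natural reading, sets each modality's scan count against the all-modality total

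*SAP*

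**What the plan says.** **S1.** Protocol section 12 promises "the OSAUS scores and the item scores after 12 months, for each of the ten scanning modalities included in the curriculum", summarised by median, IQR, minimum and maximum; sections 2b and 7 list the same two parts. SAP section 5.2 uses the same summaries but only for "the OSAUS item scores at follow-up, for each of the ten scanning modalities included in the curriculum". Both versions report follow-up only.

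**The modality score.** SAP section 5.1 still defines it: "for each scanning modality a total score from 7 to 35 points may be achieved". No outcome in SAP section 5 then reports it, and the models in section 9 are for sum scores and item scores.

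**S7.** The protocol plans a linear regression of OSAUS score on scan counts by modality, without saying which OSAUS score. The SAP replaces this with a graph of "total number of performed POCUS examinations for each of the ten scanning modalities included in the curriculum and OSAUS sum score at follow-up".

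**The sum score.** The SAP gives no formal definition. In P2 (section 5.1), each GP's summarised follow-up score "will be compared to the OSAUS sum score at baseline", which is the total over ten modalities. S8 to S10 use the same term with no reference to single modalities.

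**What stays by modality.** The SAP keeps the item scores (S1), self-rated competence (S3), and the proportion of GPs reaching "a minimum OSAUS item score of three for all seven items for each of the ten scanning modalities at follow-up" (S2).

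**Timing.** SAP section 1 reports data collection in the past tense, ending on 22 January 2024. Protocol section 20a had promised a SAP uploaded before the primary outcome data were collected.

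**The concern.** The modality is the unit in which GPs are taught, examined and asked to judge themselves. Its 7-35 score lies between 70 separate item summaries (7 items by 10 modalities) and a single total per GP. A pre-specified secondary outcome that drops out without explanation, in a plan written as though the data were in hand, leaves the report open to a charge of selective reporting, whatever the reason.

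S7 addresses a question that the protocol's background raises: how many examinations are needed to keep the skill. The study set up ten modality-specific fee codes, so counts are available by modality. If each count is plotted against a total that comes mainly from nine other modalities, a real link within one modality may look weak or absent.

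**Working it through.** **The plan's own figures.** 80% of 18 is 14.4, given as 15 GPs. 15 x 10 = 150 OSAUS forms at follow-up. Both agree with section 14 of the protocol and section 7 of the SAP. Neither document gives a power or precision figure to reproduce.

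**Step 1: weight of one modality.** The total runs from 10 x 7 = 70 to 10 x 35 = 350. A fall of 7 points in one modality is 7/35 = 20% of that modality's maximum but 7/350 = 2% of the total's. A gain of 7/9 = 0.78 point in each of the other nine cancels it in P2.

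**Step 2: can the item summaries stand in for the modality score?** Medians do not add up. In 5,000 simulated sets of 15 GPs (assumed item mean 3.5, between-GP and residual SD 0.7 each, scores rounded to 1-5), the seven item medians failed to sum to the median modality score in 69% of sets, by up to 5 of 35 points. S2 reduces each modality to pass or fail.

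**Step 3: dilution in S7, if the sum score is the all-modality total.** Assume equal SDs for the ten modality scores. Let r be the correlation of a modality's count with its own score, x its correlation with each of the other nine scores, and c the correlation between modality scores. Then

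corr(count, total) = (r + 9x) / sqrt(10 + 90c).

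The documents give none of r, x or c. With r = 0.5 assumed:

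| Assumption on x | c | Calculation | Correlation with total |
|---|---|---|---|
| Scores uncorrelated, x = 0 | 0 | 0.5/sqrt(10) | 0.16 |
| Count acts only through its own score, x = rc = 0.15 | 0.3 | 1.85/sqrt(37) | 0.30 |
| Same, x = rc = 0.30 | 0.6 | 3.2/sqrt(64) | 0.40 |
| Count unrelated to the other nine, x = 0 | 0.3 | 0.5/sqrt(37) | 0.08 |
| Same, x = 0 | 0.6 | 0.5/sqrt(64) | 0.06 |
| Counts correlate 0.6 across modalities, x = 0.5 x 0.6 = 0.30 | 0.3 | 3.2/sqrt(37) | 0.53 |

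The 0.08 and 0.06 rows are an extreme case. At c = 0.6, x = 0 implies standardised coefficients of about +1.13 on the own score and -0.12 on each of the others: for a given own-modality score, more scans would go with worse scores elsewhere. The last row applies if GPs who scan often do so in every modality.

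**Step 4: what 15 GPs can show.** Two-sided p < 0.05 at n = 15 needs |r| of about 0.51.

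**The case against.** Four stronger readings are tempting, and the documents do not support them.

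- *Modality-level skill can no longer be seen.* It can, in part: S1 items, S2 and S3 all remain by modality, and section 9 of the SAP may cover item-level models. What is lost is the modality score itself.
- *The SAP removed the view of skill kept or lost in each modality.* It did not. Protocol S1 was also follow-up only, and change by modality was never a listed outcome. Reporting it would be an addition.
- *S7 definitely uses the all-modality total.* The term is undefined. Section 9 contrasts sum scores with item scores, which would also fit a sum of seven items, and the reference to ten modalities in S7 could govern both axes. P2, and the use of the same term in S8 to S10, make the all-modality reading the more natural one but do not settle it. The protocol was no clearer.
- *The score was dropped because of what the data showed.* Nothing in the documents says so. Section 1 describes the SAP as elaborating the protocol's analyses, and parts of sections 5.2 and 6 keep the future tense. The supported statement is that the change is unexplained and appears in a document that describes collection as complete.

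It is also fair to object that 15 GPs would not give a significant result even without dilution, since the assumed 0.5 falls just short of 0.51, and that S7 in the SAP is a graph with no test. That stands: the gain from the fix is a plot that addresses the question, not a significant result. These are secondary, descriptive outcomes, and P1, P2, the sample size and the significance level are unaffected.

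**Conclusion.** The concern holds in two parts. The S1 part is firm and needs no assumption: one of its two pre-specified components is missing from the SAP, without a reason, while the SAP still defines the score in question. The remaining modality-level outcomes do not reproduce it.

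The S7 part is conditional. If the sum score means the all-modality total, each plot pairs a modality's count with an outcome in which that modality is one tenth. Dilution is then possible but not certain. For an assumed own-modality correlation of 0.5, the neutral cases give 0.16 to 0.40, and the range over the assumptions tried is 0.06 to 0.53. The documents do not show which applies. If the seven-item score was meant, there is no dilution, but the term still needs a definition.

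**What to change.** 1. Restore the modality OSAUS score (7-35) to S1 at follow-up, beside the item scores, as the protocol states; or record why it was withdrawn and when.
2. Define the OSAUS sum score once in SAP section 5.1, and use a different name for the modality score.
3. In S7, plot each modality's scan count against the same modality's OSAUS score. Keep the all-modality sum for a plot against total scans.
4. As an addition that serves the aim of maintained competence, and not as a restoration, report the baseline modality score and its paired change with a 95% CI, labelled descriptive. Step 1 of the working shows why the total alone can hide an offsetting loss.

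The cost is about ten table rows and a changed axis in ten plots. SAP section 5.1 says the OSAUS scores were collected at both time points, so no new data are needed.

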Secondary outcome 6 (S6): For GPs, participating in a POCUS quality assurance program, the test scores in the online quiz at months 3, 6, 9 and 12 after baseline.

Secondary outcome 7 (S7): For GPs, participating in a POCUS quality assurance program, the association between OSAUS score at 12 months and total number of performed POCUS examinations for each of the ten scanning modalities included in the curriculum.

Secondary outcome 8 (S8): For GPs, participating in a POCUS quality assurance program, the association between OSAUS score at 12 months and the number of completes quizzes in the quality assurance program.

Secondary outcome 9 (S9): For GPs, participating in a POCUS quality assurance program, the association between OSAUS score at 12 months and the test score in the quizzes in the quality assurance program.

Secondary outcome 10 (S10): For GPs, participating in a POCUS quality assurance program, the association between OSAUS score at 12 months and the OSAUS score at baseline.

Secondary outcome 11 (S11): For GPs, participating in a POCUS quality assurance program, their evaluation of the program after 12 months.

8 Trial design

This is a cohort study designed as a follow-up for a hybrid effectiveness-implementation study (ClinicalTrials.gov Identifier: NCT05274581). In the previous study, 18 GPs attended an ultrasound course targeted to office-based GPs. The ultrasound course consisted of three teaching seminars over three months (Marts – June 2022), a curriculum of 10 POCUS applications, an online learning platform providing educational support before, during and after the teaching sessions (see Figure 1). At the end of the ultrasound course (June 2022) and again 3 months after the ultrasound course (September 2022), all participants had their scanning competences within the 10 POCUS applications assessed by external experts. These experts were blinded to the participants previous experience and learning process. The assessment of scanning competence was done using the OSAUS assessment tool¹⁴. Following this study participants have implemented POCUS in their clinical practice, where they use POCUS as part of the patient examination.

Before data collection starts, this trial will be registered on *clinicaltrials.gov*.

Methods - Participants, interventions, and outcomes

9 Study settings

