The GPs are asked to declare any additional POCUS course activity or education during the study.

12 Outcome measures

Background characteristics of participating GPs

At baseline the following participant characteristics will be collected: Age (years), gender (M, F, other), previous use of ultrasound (number of months with regular use), previous ultrasound courses of minimum 1 day duration (yes/no), scanner type (low range, mid range, high end), type of practice (collaboration, partnership, solo), location of practice (urban, rural, mixed), number of patients assigned to the practice, and number of GPs working in the practice.

In addition, the results from the OSAUS assessment of scanning competences conducted on all participants in September or October 2022 will be included.

The OSAUS assessment tool has been developed and validated as a generic tool for assessing scanning competence¹⁴. The OSAUS scale consists of seven items: 'indication for the examination', 'applied knowledge of ultrasound equipment', 'image optimization', 'systematic examination', 'interpretation of images', 'documentation of the examination' and 'medical decision-making' and each item is rated using a five-point Likert-scale with descriptions of performance ranging from very poor (score = 1) to excellent (score = 5). All items are weighted equally, as high inter-item correlation have been found previously¹⁵. Hence, for each scanning modality a total score from 7 to 35 points may be achieved.

The OSAUS ultrasound competence assessment tool have been developed as a generic tool to assess ultrasound competence across medical specialities. The assessment tool was developed through a Delphi study¹⁴ and it has been used to assess clinicians' ability to transfer learning from an ultrasonography course into diagnostic performance on patients. Furthermore, the tool has been found valid and reliable to distinguish between novice POCUS users and experts¹⁶.

For the primary outcome(P1) and secondary outcomes (S1-S2) we will use the Objective Structured Assessment of Ultrasound Skills (OSAUS) score scored after 12 months. For the primary outcome (P2) we will use the OSAUS score at baseline and at 12 months.

Primary outcomes:

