# 9. Statistical analysis

The analysis of OSAUS sum scores and item scores will be performed using linear regression or repeated measures ANOVA, with participants being the random effect. Cohen's d will be used to estimate effect size. To account for interrater variation, we will calculate an average score for each expert and adjusted results so that experts have the same average score. Sensitivity analyses will be performed and the results of both complete case and adjusted analyses will be reported. Distributions of baseline values will be presented as mean (SD) and median [IQR] for continuous or n (%) for categorical variables. Fisher's exact test will be used to compare out sample to the general population of GPs in Denmark. OSAUS scores will be presented in tables as summarized complete case (raw data) and statistical optimal data (including imputation and adjustment for expert variation). Results with p-values < 0.05 will be considered statistically significant. All statistical analyses will be performed using STATA version 18 (StataCorp, Texas, USA).

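### For S7–S9 the SAP describes plots where the protocol planned regressions, without withdrawing them, and neither document uses the baseline OSAUS score already collected

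*SAP*

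**What the plan says.** Protocol section 12 (Outcome measures) says of S7, S8 and S9: "we will use a linear regression model to test associations between OSAUS score after 12 months" and, in turn, the number of scans per modality, the number of completed quizzes and the quiz scores. It names no other model term.

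SAP 5.2 says of S7: "we will graphically illustrate the relationship between total number of performed POCUS examinations for each of the ten scanning modalities", set against the OSAUS sum score at follow-up. S8 and S9 have parallel sentences for completed quizzes and quiz score. No model, slope or interval is mentioned.

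Three other statements bear on whether the regressions survive:
- SAP 1: "This document elaborates on these intended analyses to be performed in the main study paper".
- SAP 9: "The analysis of OSAUS sum scores and item scores will be performed using linear regression or repeated measures ANOVA", with participant as a random effect. The sentence is not tied to particular outcomes and names no exposure or covariate.
- SAP 9 also has a general rule: "Results with p-values < 0.05 will be considered statistically significant".

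Baseline OSAUS is available. Protocol section 8 reports that "all participants had their scanning competences within the 10 POCUS applications assessed by external experts", at the end of the course and again three months later. SAP 1 makes the three-month assessment the baseline of this study, and Protocol section 12 confirms that "the results from the OSAUS assessment of scanning competences conducted on all participants in September or October 2022 will be included". In the SAP, baseline OSAUS enters P2 and S10 ("we will graphically illustrate the relationship between the OSAUS sum score at baseline and OSAUS sum score at follow-up") but not S7–S9. The only adjustment described in SAP 9 is for differences between assessors.

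**The concern.** The study asks whether competence is maintained, so where each GP started matters. A GP who began the year more skilled may also score higher in the quizzes or scan more. Follow-up OSAUS would then rise with quiz score or volume even if neither had any effect. If weaker GPs practised more, the raw relationship would instead hide an effect.

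The three outcomes differ in how likely such a link is:
- **S9:** plausible, because Protocol 11a classifies each quiz question by OSAUS dimension.
- **S7:** possible only. Protocol 6 relates low scan frequency to the patients seen, which need not depend on skill.
- **S8:** the documents suggest no mechanism.

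Protocol 6 notes how little is known about the scan volume needed to keep skills, so readers may look to S7 for an answer. Protocol 20b promises sub-analyses of the educational elements, to be defined in the SAP. The SAP defines none, and S7–S9 are the nearest it comes. A plot of about 15 points without an interval does not show how uncertain the relationship is.

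The outcome for S7 is also unclear. P2 uses the OSAUS sum score for the total over ten modalities, while S7 is stated per modality.

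**Working it through.** **The plan's own figure.** 18 × 0.80 = 14.4, rounded up to 15 GPs; 15 × 10 modalities = 150 OSAUS forms. Both reproduce. The documents give no figure for S7–S9.

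**S7 score.** One modality runs from 7 to 35 points. Ten modalities run from 10 × 7 = 70 to 10 × 35 = 350. Plotting one modality's scans against its own score is a different analysis from plotting them against the total.

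**Spurious relationship with no true exposure effect.** The inputs are assumptions, since the documents give none: rb = correlation of baseline skill with follow-up OSAUS, 0.5–0.7; rv = correlation of baseline skill with exposure, 0.3–0.5. Then raw r = rb × rv. The table adds the share of studies with p < 0.05 (n = 15, 40,000 simulated data sets per setting).

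| rb | rv | raw r | p < 0.05, unadjusted |
|---|---|---|---|
| 0.5 | 0.3 | 0.15 | 8.2% |
| 0.5 | 0.4 | 0.20 | 11.3% |
| 0.5 | 0.5 | 0.25 | 14.8% |
| 0.6 | 0.3 | 0.18 | 9.8% |
| 0.6 | 0.4 | 0.24 | 13.9% |
| 0.6 | 0.5 | 0.30 | 19.1% |
| 0.7 | 0.3 | 0.21 | 11.3% |
| 0.7 | 0.4 | 0.28 | 17.2% |
| 0.7 | 0.5 | 0.35 | 25.5% |

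With baseline skill in the model the mean slope lies between -0.003 and 0.002 and the rate between 4.9% and 5.3%. If rv = 0, raw r is 0 and the unadjusted rate is 5%. If rv is negative, raw r changes sign.

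**Imperfect baseline measurement.** With reliability λ for baseline OSAUS (assumed), the residual slope is rb·rv·(1 − λ)/(1 − λ·rv²).
- λ = 0.8, rb = 0.7, rv = 0.5: 0.35 × 0.2/0.8 = 0.088.
- λ = 0.9, same correlations: 0.35 × 0.1/0.775 = 0.045.

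Over the grid, adjustment removes 75–78% of the bias at λ = 0.8 and 87–89% at λ = 0.9.

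**Precision.** Fisher-z 95% interval around r = 0 at n = 15: ±tanh(1.96/√12) = ±0.51. Around r = 0.35 it is -0.20 to 0.73.

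Adjusted/unadjusted SE ratio = √[(1 − rb²)/((1 − rv²)(1 − rb²rv²)) × 13/12].
- rb = 0.7, rv = 0.3: √[0.51/(0.91 × 0.956) × 13/12] = 0.80.
- rb = 0.5, rv = 0.5: √[0.75/(0.75 × 0.9375) × 13/12] = 1.08.

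Half-widths of the 95% interval for a standardised slope are 0.56–0.60 unadjusted and 0.47–0.63 adjusted.

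**Number of estimates.** Ten modalities for S7, plus S8 and S9, make 12 exposures; each reported twice gives 24.

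**The case against.** **Plots only is probably what the SAP means.** S7–S10 are all reworded in the same way, which looks deliberate. The participant random effect in SAP 9 suits repeated scores per GP, whereas S8 and S9 have one follow-up sum score each. This stands as the more natural reading. It does not settle the matter, because SAP 1 says the SAP elaborates on the protocol's analyses and nothing is withdrawn.

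**Plots carry no test.** On that reading the 8–25% rates do not apply. This stands. They matter only if the regressions are run and tested.

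**The confounding is assumed.** This stands too. The grid uses positive links only, and the documents support neither a size nor a sign. S8 takes only the values 0 to 4, and GPs who miss quizzes are reminded and contacted, so it may hardly vary.

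**The raw association is what the protocol defines.** Neither document makes a causal claim for S7–S9. For S9 the raw relationship is also informative as agreement between two measures: Quiz 4 was taken in October/November 2023, and follow-up OSAUS began on 30 November. Baseline adjustment would remove part of that. This is a reason to report both estimates, not to omit the adjusted one.

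**Many wide intervals can mislead.** This is a real cost, and the reason to make no significance claims.

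A reader might also count chance findings. With no association at all, 31–40% of studies would show |r| above 0.51 in at least one of the ten S7 plots (between-modality correlation 0–0.7, assumed). That is multiplicity. Baseline adjustment does not reduce it, so it is no argument for adjusting.

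**Conclusion.** The protocol and SAP differ on S7–S9, and the SAP does not say whether the regressions are replaced. On either reading, baseline OSAUS is collected but unused in these three outcomes. The raw relationship may therefore overstate or hide a practice or quiz effect.

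Under the assumed positive correlations the spurious r is 0.15–0.35. It is zero without a link and of opposite sign with a negative one. The ±0.51 interval does not depend on those correlations, only on n = 15.

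Three stronger inferences are tempting, and the documents support none of them:
- That the regressions have definitely been dropped, or definitely kept. The text permits both.
- That starting skill will inflate these relationships. The documents give no correlations, and for S8 no mechanism.
- That the study faces an 8–25% false-positive rate. This needs both formal testing and the assumed correlations.

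P1 and P2 are unaffected. This is an improvement to consider for exploratory secondary outcomes, held with medium confidence.

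**What to change.** - State whether the protocol regressions for S7–S9 still apply, and keep the plots.
- For S7 and S9, report the slope with a 95% interval twice: unadjusted (the association the protocol defines) and adjusted for baseline OSAUS.
- For S8, do the same only if completed quizzes vary enough; otherwise report counts and say why.
- For S7, specify the modality's own 7–35 score and that modality's own baseline.
- Label all of these exploratory, exempt them from the p < 0.05 rule in SAP 9, and state that no causal reading is intended.

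This needs no new data and a few lines of code. The costs are up to 24 estimates, one residual degree of freedom in each adjusted model (15 − 2 = 13 to 15 − 3 = 12) and wide intervals. Precision may improve or worsen (SE ratio 0.80–1.08 over the assumed grid). Adjustment is only partial, because baseline OSAUS carries rater error.
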